8.4. Treatment Visit (Day 0)

Prior to the Treatment Visit, the clinical team will contact study participants to confirm if their pre-treatment swab results meet criteria for enrolling in the AD SA+ or AD SA- group. If the enrollment goal(s) for AD SA+ or AD SA- have been met, the participant will be identified as a screen failure.

The purpose of the Day 0 Treatment Visit is to complete study treatment, application of ShA9 and placebo. The following procedures, assessments, and laboratory measures will be conducted at the Treatment Visit:

- Interim medical history and physical exam, including assessment of AD severity (L-EASI, SCORAD, and local Pruritus NRS) by study physician or other qualified medical professional
- Pregnancy status of participant and partner of participant, as applicable, and urine pregnancy test (female participants only), per [Section 8.2](#)
- Assessment of concomitant medications
- Vital Signs
- Randomization
- Identification of measured non-lesional site on the participant's face, including photograph, and skin swab collection for the assessment of ShA9 spread. Two non-lesional swabs will be collected from the participant's face.
- Skin Swab Collections from the ventral arms, to assess live bacteria by CFU, bacterial DNA by qPCR, and antibiotic sensitivity to penicillin G, tetracycline, and erythromycin. Two lesional and two non-lesional swabs will be collected from each ventral arm (8 swabs total).
- *S. hominis* A9 and placebo application
- Participants will remain in clinic for up to 6 hours following the application of investigational product. Additional skin swabs will be collected from the participant's arms at 15 minutes, 1, 2, 4, and 6 hours post-application. Two lesional and two non-lesional swabs will be collected from each ventral arm for a total of eight swabs at each time point.
- Assessment of AEs

At the conclusion of this visit, participants will be reminded to use Dove moisturizing soap, whenever they shower, but to avoid the arms, until after their last in-clinic visit is complete. Participants will be allowed to use Cetaphil® lotion to moisturize if necessary. Participants will be given instructions regarding restrictions on bathing/showering, exercise, and use of emollient. Participants will be reminded to refrain from swimming in chlorinated pools and hot tubs and to refrain from the use of prohibited medications, for the duration of their study participation. Participants will be asked to try to restrict pets from licking the treated areas. Female subjects of child-bearing potential will be instructed to use an effective method of birth control or abstinence.

Participants will be given a handcard describing the symptoms of skin and systemic infections and will be told to contact the research clinic if they experience any of the listed symptoms. The participants will be instructed to take the handcard with them should they seek medical care at another facility. The handcard will state that the patient is

currently in a study involving the application of non-pathogenic bacteria to the skin and will instruct them to call the research site if an infection of the skin or blood is suspected.

8.5. Follow-Up Visits (24 Hour and Days 3, 10, 17 and 24)

After the Treatment Visit, participants will be asked to return to the clinic for a follow up 24 Hours after the Day 0 Visit and on Days 3 (\pm 1 day), 10 (\pm 1 day), 17 (\pm 2 days), and 24 (\pm 2 days). The purpose of the follow-up visits is to assess *S. aureus* and CoNS bacteria abundance and AEs.

The following procedures, assessments, and laboratory measures will be conducted at each visit:

- Assessment of AEs
- Assessment of AD severity (L-EASI, SCORAD, and local Pruritus NRS) by study physician or other qualified medical professional
- Pregnancy status of participant and partner of participant, as applicable
- Assessment of concomitant medications
- Vital Signs
- Skin Swab Collections, (lesional and non-lesional) from the ventral arms, to assess live bacteria by CFU and bacterial DNA by qPCR and non-lesional skin swab collection from the participant's face for the assessment of ShA9 spread. Two lesional and two non-lesional swabs will be collected from each ventral arm, and two additional non-lesional swabs will be collected from the face (10 swabs total).
- Lesional skin swabs taken at the last Follow-Up Visit will also be analyzed for antibiotic sensitivity to penicillin G, tetracycline, and erythromycin.

At the conclusion of each visit, participants will be reminded to use Dove moisturizing soap, whenever they shower, but to avoid the arms, until after their last in-clinic visit is complete. Participants will be given instructions regarding restrictions on bathing/showering, exercise, and use of emollient. Participants will be reminded to refrain from swimming in chlorinated pools and to refrain from the use of prohibited medications. Female participants of childbearing potential will be instructed to use an effective method of birth control or abstinence.

Upon completion of the Day 3 Visit, a participant will be notified prior to their next scheduled follow-up visit if they need to return to the clinic. A participant will not be required to complete the remaining follow up clinic visits (Day 10 through Day 24) if the lesional swabs from both arms collected at their most recent prior visit are CoNS negative, defined as below baseline density measured before application of ShA9 + 100 CFU/cm². The lesional skin swabs taken at the last completed Follow-Up Visit will be used in analysis for antibiotic sensitivity to penicillin G, tetracycline, and erythromycin. Once a participant completes his/her required follow up clinic visits, he/she may resume prohibited medications as described in [Section 7.3](#), as needed, and may use his/her choice of soap and emollient.

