Participants who complete the pre-treatment phase (7 ± 1 days total) and meet enrollment criteria for AD SA+ or AD SA-, will come back to clinic for their Treatment Visit (Day 0). Participants must be cultured to determine *S. aureus* colonization status. Given the rates of *S. aureus* colonization, it is likely that enrollment will be complete for the AD SA- group before the AD SA+ group. Once the enrollment goals for AD SA+ or AD SA- are met, additional participants will be identified as screen failures. During the Treatment Visit, the participant will have ShA9 applied to their right or left ventral arm and placebo applied to their contralateral ventral arm. The assignment of ShA9 and placebo to the dominant and non-dominant arms will be randomized. Prior to the application of the ShA9 and placebo treatments, skin swabs will be collected from the lesional and non-lesional sites on the ventral arms and one non-lesional site on the participant's face. A blinded clinical team member will apply the designated treatment to each arm, and additional swabs will be collected from the arms 15 minutes and 1, 2, 4, and 6 hours after application. Participants will return to the clinic 24 hours after application (24 Hour Visit) and on Days 3, 10, 17, and 24 for the assessment of AEs and the collection of skin swabs from the identified target sites, as needed. After completion of the Day 3 Visit, a participant will not be required to complete the remaining follow up clinic visits (Day 10 through Day 24) if their lesional swabs from both arms (right and left) are CoNS negative, defined as CoNS below baseline density measured before application of ShA9 + 100 CFU/cm². All randomized participants will complete a final End of Study Phone Visit on Day 31 to assess safety and disease status.

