3.5. Stratification, Randomization, and Blinding/Masking

Arm dominance may affect the spread of ShA9 to the contralateral arm; therefore, the design will stratify by arm dominance, with the dominant arm being the right arm for right-handed participants, and the left arm for left-handed participants. A minimum of 13 participants with *S. aureus* colonized lesions on their ventral arms and a minimum of 7 participants with *S. aureus* negative lesions on their ventral arms will be randomized to one of two treatment groups: 1) ShA9 dominant and placebo non-dominant or 2) ShA9 non-dominant and placebo dominant. It is anticipated that enrollment will be higher for right-handed participants as that is the more dominant arm in the general population; enrollment will not target equal numbers of right-handed and left-handed participants. Randomization will be performed centrally at the Statistical and Clinical Coordinating Center (SACCC) using a stratified randomization design.

This is an open-label study, as all participants will receive active and placebo treatment. However, investigators, all investigational site staff, including those responsible for preparing/administering the investigational product, and all participants in this study will be blinded as to which arm received which treatment. Laboratory staff performing the mechanistic assays will be unblinded to which arm received which treatment, to ensure the correct dilutions can be applied to each sample prior to completing assays for quantification of live bacteria by culture (*S. aureus* and CoNS) and bacterial DNA (*S. hominis* A9) by qPCR (Refer to [Section 9](#)).

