4. Upon completion of the Day 3 Follow-Up Visit, a participant will be notified prior to their next scheduled follow-up visit if they need to return to the clinic. A participant will not be required to complete the remaining follow up clinic visits (Day 10 through Day 24) if the lesional swabs from both arms (right and left) collected at their most recent prior visit, have CoNS CFU below baseline density measured before application of ShA9 + 100 CFU/cm².

Targeted Investigation of Microbiome Elimination

Version 2.0

08Apr2022

Atopic Dermatitis Research Network (ADRN)

Confidential

Page 58 of 58

5. If disease activity increases, participants experience signs and symptoms as described on the instructional handcard, or other concerns arise between regularly scheduled visits, participants may be asked to return to the study site for an Unscheduled Visit.
6. An abbreviated Medical History will be collected.
7. AD disease severity will be assessed using the Investigator Global Assessment (Screening only), local Eczema Area and Severity Index (L-EASI) on the arms, SCORing Atopic Dermatitis (SCORAD), and local Pruritus Numerical Rating Scale (NRS).
8. A urine pregnancy test will be completed for all female participants of child bearing potential who do not self-report as pregnant at the Screening and Treatment Visits.
9. Vital signs will include temperature, heart rate, respiration rate, systolic blood pressure, and diastolic blood pressure. Growth parameters (height and weight) will only be collected at the Screening Visit.
10. Skin swab collection from the participant's ventral arms will occur during each visit, and skin swab collection from the participant's face will begin at the Treatment Visit.
11. Lesional and non-lesional sites will be identified on the participant's ventral arms for skin swab collection. Digital photographs of the lesional and non-lesional swab sites will be taken prior to swab collection. Each photograph will include a ruler so the scale of the sites can be determined. These sites will be swabbed at subsequent visits.
12. A non-lesional site will be identified on the participant's face for skin swab collection. A digital photograph of the non-lesional swab site will be taken prior to swab collection. The photograph will include a ruler so the scale of the site can be determined. This site will be swabbed at subsequent visits.

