7.2 Reporting of Swab Results

Prior to the application of the ShA9 and placebo treatment, skin swabs will be collected from the lesional and non-lesional sites on the ventral arms and one non-lesional site on the participant's face. After IP administration to each arm, additional swabs will be collected from the arms 15 minutes and 1, 2, 4, and 6 hours after application. Participants will return to the clinic 24 hours after application (24 Hour Visit) and on Days 3, 10, 17, and 24 for the collection of skin swabs from the identified target sites, as needed. However, after completion of the Day 3 Visit, a participant will not be required to complete the remaining follow up clinic visits (Day 10 through Day 24) once their lesional swabs from both arms (right and left) are CoNS negative, defined as below baseline density measured before application of ShA9 + 100 CFU/cm². The collected swabs will be used to assess the following:

1. *S. aureus* (CFU/cm²)
2. Coagulase negative staphylococcal species (CoNS) (CFU/cm²)
3. *S. hominis* A9 (CFU/cm²)
4. Combined *S. hominis* A9 (CFU/cm²)
5. Combined bacteria DNA (CFU/cm²)
6. Antibiotic-sensitive CoNS

S. aureus will be measured by counting CFUs on the Baird-Parker agar plate. Coagulase negative staphylococcal species (CoNS) will be measured by counting CFUs on the mannitol salt agar with egg yolk plate. CFUs of *S. hominis* A9 will be estimated from total CoNS CFU × % of *S. hominis* A9 positive colonies. Abundance of bacterial DNA from total staphylococcus (G-staph), *S. aureus*, *S. hominis*, and Sh-lantibiotic will be quantified by qPCR. Antibiotic-sensitive CoNS will be estimated from [(CFU without antibiotic containing plate - CFU with antibiotic containing plate)/(CFU without antibiotic containing plate)].

Descriptive statistics and listings by participant of swab results will be presented. Swab results will be plotted to show the trajectory of results over time. Data will be plotted as a spaghetti plot where each

participant's values will be plotted and connected by line segments, forming one line per participant. Plots will also indicate arm dominance per participant.

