7.3.1 Computation of the Primary Endpoint

Time-to-CoNS elimination is defined as the time from Day 0 to the first occurrence of a value below baseline density measured before application of ShA9 + 100 CFU/cm². The time to event for participants who did not reach CoNS CFU below baseline density measured before application of ShA9 + 100 CFU/cm² during the study will be right-censored.

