7.4.2 Analyses of Secondary Endpoints

Secondary endpoint #1 will be analyzed using the same approach as described for the primary analysis of the primary endpoint (see Section 7.3.2). Median survival time along with 95% CI will be constructed based on a log-log transformed CI for the survivor function $S(t)$. A graph of the Kaplan-Meier survival curve will be presented, and rates at fixed days will be derived (Therneau, et al., 2000). Furthermore, estimation of the hazard rate and 95% CI will be produced using a parametric survival model.

The summary of all treatment-emergent adverse events and treatment-emergent serious adverse events for secondary endpoint #2 will be provided by system organ class, high-level term, and preferred term in descending order of frequency.

Secondary endpoint #1 will be run on the modified intent to treat sample and re-run using the per-protocol sample if this differs from the former. Secondary endpoint #2 will be run on the safety sample.

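### Release from the Day 10 to 24 visits depends on lesional swabs alone, so non-lesional survival times after Day 3 can be cut off by the same participant's lesional result

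*Protocol*

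**What the plan says.** Every statement of the release rule names lesional swabs only. Protocol 3.1 releases participants after Day 3 "if their lesional swabs from both arms (right and left) are CoNS negative". Protocol 8.5 does so "if the lesional swabs from both arms collected at their most recent prior visit are CoNS negative", and footnote 4 of the Schedule of Events (Appendix B) likewise refers to the most recent visit: "if the lesional swabs from both arms (right and left) collected at their most recent prior visit". SAP 7.2 repeats the condition: "once their lesional swabs from both arms (right and left) are CoNS negative". Note 4 to Protocol Figure 3.1 and SAP 14.1 and 14.2 agree.

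Both skin types are sampled at one visit: "Two lesional and two non-lesional swabs will be collected from each ventral arm, and two additional non-lesional swabs will be collected from the face" (Protocol 8.5). A skipped visit therefore loses the non-lesional result as well.

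Secondary objective 1 concerns non-lesional survival in SA+ participants over up to 24 days. SAP 7.4.2 states: "Secondary endpoint #1 will be analyzed using the same approach as described for the primary analysis of the primary endpoint". That means Kaplan-Meier plus a parametric hazard. Under SAP 7.3.1, the times of participants who do not reach the threshold "during the study will be right-censored". SAP 7.1.1 says that missing data are in general not imputed. SAP 12 corrects the analysis of secondary endpoint 1 but leaves the release rule as it is.

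**The concern.** Kaplan-Meier with right-censoring assumes that people censored at a given time have the same outlook as those still followed. Here censoring of the non-lesional time is triggered by another outcome in the same person. If people who clear lesional skin quickly also tend to clear non-lesional skin quickly, those released early are the ones closest to a non-lesional event. The people left at risk are then the slow clearers, and the curve stays too high. Without such correlation the estimate is unbiased, but events are lost.

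The documents expect the affected case to be common. Protocol 1.4 reports that in the earlier trial lesional CoNS was back near baseline on Days 4 and 7, while non-lesional CoNS stayed above vehicle (group-level data, repeated application). Exploratory endpoint 5, lesional against non-lesional within a person, is the most exposed, because the lesional event itself can end observation of its pair. The study is meant to inform dosing frequency, so how long the strain lasts on each skin type matters.

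**Working it through.** **Inputs from the documents.** Lesional hazard 0.15/day for planning and 0.09/day from the earlier study; 13 SA+ participants (Protocol 13.7, SAP 11). Visits on Days 3, 10, 17 and 24 (Protocol 8.5).

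**Assumptions.** Exponential times; non-lesional hazard λ of 0.05, 0.09, 0.15 or 0.3/day; released participants do not return; the placebo-arm lesional swab is always negative unless stated. None of these comes from the documents.

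**1. The plan's own figure.** For 9 events and hazard 0.15, the exact 95% interval has width 0.15/18 × (31.526 − 8.231) = 0.194, as stated. It concerns the lesional primary endpoint and is not in question here.

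**2. Attendance, no correlation.** Expected attendance of the 13:
- Day 10: 13·e^(−0.45) = 8.3
- Day 17: 13·e^(−1.5) = 2.9
- Day 24: 13·e^(−2.55) = 1.0

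The share released after Day 3 is 1 − e^(−0.45) = 36%.

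**3. Observed non-lesional events, no correlation.** Let N and L be the non-lesional and lesional survivor functions. The observed share is

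1 − N(3) + L(3)[N(3) − N(10)] + L(10)[N(10) − N(17)] + L(17)[N(17) − N(24)].

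At λ = 0.05: 0.139 + 0.638×0.254 + 0.223×0.179 + 0.078×0.126 = 0.351, or 4.6 of 13. Full follow-up gives 1 − e^(−1.2) = 0.699, or 9.1 of 13.

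| λ per day | Observed share (of 13) | Full follow-up |
|---|---|---|
| 0.05 | 35% (4.6) | 70% |
| 0.09 | 51% (6.7) | 88% |
| 0.15 | 66% (8.6) | 97% |
| 0.3 | 83% (10.8) | 100% |

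Kaplan-Meier stays unbiased: at λ = 0.05, 0.861 × 0.7047³ = 0.301 = e^(−1.2). The cost is precision. The Wald width 2×1.96×0.05/√events rises from 0.065 (9.08 events) to 0.092 (4.57 events).

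**4. Positive correlation.** With a shared gamma frailty of mean 1 and variance 1, the joint survivor function is S(a,b) = 1/(1 + 0.15a + λb) for lesional time a and non-lesional time b. The hazards are now conditional on the frailty, so these populations differ from those in step 3. Release after Day 3 is 1 − 1/1.45 = 31%, and attendance is 9.0, 5.2 and 3.7.

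Under the release rule, Kaplan-Meier estimates

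N(3) × S(3,10)/S(3,3) × S(10,17)/S(10,10) × S(17,24)/S(17,17).

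At λ = 0.05: 1/1.15 × 1.60/1.95 × 3.00/3.35 × 4.40/4.75 = 0.59. The true value is 1/(1 + 1.2) = 0.45.

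| λ | Day 24 KM | True | KM, placebo arm negative half the time |
|---|---|---|---|
| 0.05 | 0.59 | 0.45 | 0.52 |
| 0.09 | 0.43 | 0.32 | 0.37 |
| 0.15 | 0.30 | 0.22 | 0.26 |
| 0.3 | 0.16 | 0.12 | 0.14 |

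The last column comes from simulation (300,000 participants per cell).

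**5. Sensitivity.**
- Frailty variance 0.5: Day 24 KM 0.50 against 0.39, 0.32 against 0.23, 0.19 against 0.13, and 0.07 against 0.05.
- Lesional hazard 0.09, λ = 0.05: without correlation, 43% of events are observed against 70%. At variance 1 the KM is 1/1.15 × 1.42/1.77 × 2.40/2.75 × 3.38/3.73 = 0.55 against 0.45.
- Gaussian copula with the marginal distributions held fixed, lesional 0.15, λ = 0.09, correlation 0.5: KM 0.20 against 0.12, and 6.8 events against 11.5.
- Exponential hazard (events over person-time), variance 1, rule against full follow-up: 0.026 against 0.031, 0.042 against 0.046, 0.062 against 0.064, and 0.099 against 0.097. It is understated mainly when clearance is slow.
- Sampling error: in simulated 13-person trials at λ = 0.05 with frailty, the SD of the Day 24 KM is 0.19 to 0.22.

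**The case against.** The strongest reply is about size. The calculation leads with the faster of the two documented lesional hazards and a placebo arm that never delays release. At 0.09/day the largest bias falls from 0.14 to 0.10, and with the placebo arm negative only half the time (at 0.15/day) to 0.07. Even the largest bias is below one SD with 13 participants. The documents give no correlation between sites, and their proposed mechanism, killing by inflamed skin, is local and does not imply a strong one. This is an estimation pilot, and the contrast between skin types has not been quantified here: SAP 7.5.2 describes no analysis for exploratory endpoints 2 to 5, and for SA+ against SA− some of the bias may cancel. The rule also says only that later visits are not required.

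All of this limits the size and is accepted. It does not remove the mechanism. The loss of events needs no correlation and remains at 0.09/day. No section plans swabs after release, and Protocol 8.5 lets released participants resume prohibited medications and their own soap and emollient, so voluntary later swabs would not be comparable. Two further limits help the plan: non-lesional clearance by Day 3 is fully observed, and anyone still positive on either arm's lesional skin keeps both sites swabbed.

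**Conclusion.** The concern holds and should be fixed. Followed as written, the plan lets the lesional result end observation of a secondary endpoint that is meant to run to Day 24, and neither document addresses it. What is certain is the rule, and a loss of non-lesional events after Day 3 whenever released participants still positive on non-lesional skin do not return. At the planning lesional hazard this could remove about half of the events if non-lesional clearance is slow (0.05/day), and about a sixth if it is fast (0.3/day). Upward bias in the non-lesional Kaplan-Meier curve, and distortion of the lesional against non-lesional contrast, require positive within-person correlation. In the frailty cases tabulated above, the bias at Day 24 runs from about 0.02 to 0.14. These figures illustrate; they do not predict.

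**What to change.** Keep the both-arms condition and add the non-lesional swabs: release a participant from the scheduled swab visits only when lesional and non-lesional swabs from both arms are below threshold. The places to change are Protocol 3.1, Figure 3.1 note 4, 8.5 and footnote 4 of the Schedule of Events, and SAP 7.2, 14.1 and 14.2. Treating both arms alike preserves the blinding in Protocol 3.5 ("all participants in this study will be blinded as to which arm received which treatment") and keeps contralateral data for exploratory endpoint 1. In both models Kaplan-Meier is then unbiased, provided the added swabs come from comparably managed skin.

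**Cost.** At most three more visits per participant, all already scheduled. Without correlation the extra visits for the 13 SA+ participants are 13 × Σ[1 − L(u)]N(u) over u = 3, 10, 17:
- λ = 0.05: 13 × (0.312 + 0.471 + 0.394) = 15.3
- λ = 0.3: 13 × (0.147 + 0.039 + 0.006) = 2.5

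For all 20 at the same hazards this is about 24 and 4. Fluctuation on placebo-arm non-lesional skin would add visits. Protocol 7.3 ties the return to prohibited medications to CoNS falling below threshold without naming the site or arm, while 8.4 and 8.5 tie soap, emollient or medications to the last or required clinic visits. The sponsor must reconcile these passages with the visit rule; no clinical rule is proposed here.

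**If the visits cannot be extended,** keep all later swabs and pre-specify bounds for the non-lesional curve: participants censored by release counted as positive through Day 24, then as cleared at their next scheduled visit. State that non-lesional estimates and lesional against non-lesional comparisons beyond Day 3 are subject to lesion-dependent censoring. This needs only SAP text, but the bounds are wide. Without correlation, Day 24 survival runs from N(24)·L(17) = 0.301 × 0.078 = 0.02 to 1 − 0.351 = 0.65 at λ = 0.05, and from 0.00 to 0.17 at λ = 0.3. Inverse-probability-of-censoring weights on ShA9-arm lesional status work only if enough participants with a cleared ShA9-arm lesion keep attending; otherwise there is nobody to up-weight. Truncating the analysis at Day 3 is not a good substitute: at λ = 0.05 only 1 − e^(−0.15) = 14% have an event by then.
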